If the experience is not covered in the CTCAE criteria, the guidelines shown in [Table 4](#) below will be used to grade severity. It should be pointed out that the term "severe" is a measure of intensity and that a severe event is not necessarily serious.

Table 4: AE Severity Grading

Severity (Toxicity Grade)	Description
Mild (1)	Transient or mild discomfort; no limitation in activity; no medical intervention or therapy required. The patient may be aware of the sign or symptom but tolerates it reasonably well.
Moderate (2)	Mild to moderate limitation in activity, no or minimal medical intervention/therapy required.
Severe (3)	Marked limitation in activity, medical intervention/therapy required, hospitalizations possible.
Life-threatening (4)	The patient is at risk of death due to the adverse experience as it occurred. This does not refer to an experience that hypothetically might have caused death if it were more severe.
Death (5)	Death related to AE

AE=adverse event.

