4.15.1 Adverse Events

For AEs and Serious AEs (SAEs), the MedDRA Version 22.1 or later will be used to code the reported events.

Treatment-emergent adverse events (TEAEs) will be tabulated and are defined as those AEs that either start or worsen in severity on or after the date/time of IP administration and on or before Day 4.

Where dates are missing or partially missing, AEs will be assumed to be treatment-emergent, unless there is clear evidence (through comparison of partial dates) to suggest that the AE started prior to IP administration or more than 4 days after IP administration.

In particular this means the following rules will be applied until a classification is given:

1. An AE with a missing start date and missing end date will be a TEAE
2. An AE with a missing start date and end date after IP administration will be TEAE
3. A start date with a missing year but month present will be assumed to have a year such that the start date is after informed consent and before Day 90. If these rules conflict then the rule 'after informed consent' prevails.
4. An AE will not be a TEAE if the start date is incomplete and
 - a. The end date of the AE is before the dosing date
 - b. The end date/time of an AE is before the dosing date/time
 - c. The day of the AE end date is missing and the month of the AE end date is before the month of dosing date
5. An AE will not be a TEAE if the AE start day of month is missing and
 - a. The last day of the AE start month is before the dosing date
 - b. The first day of the AE start month is more than 4 days after dosing

All AE summaries will provide the number of patients reporting at least one AE and the total number of events reported.

The following summaries will be provided:

- A summary of the number and percentage of patients reporting an AE, including counts of TEAEs, IP-related TEAEs, SAEs and IP-related SAEs.

PAREXEL International

Blue Earth Diagnostics
BED-PSMA-301

Statistical Analysis Plan

- A summary of the number and percentage of patients reporting a TEAE by SOC, and PT
- A summary of the number and percentage of patients reporting a TEAE by Common Terminology Criteria for Adverse Events (CTCAE) grade, SOC and PT
- A summary of the number and percentage of patients reporting a TEAE by causality, SOC and PT

Adverse event summaries will be ordered in terms of decreasing frequency for SOC, and PT within an SOC and then alphabetically for SOC, and PT within SOC.

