For each patient and each adverse event, the worst CTCAE Toxicity grade (Version 5) recorded will be attributed and used in the by-severity summaries. Similarly, the worst causality (most related to treatment) will be attributed and used in the by-causality summaries. If CTCAE is missing for, the missing category will be used as worst category. If causality is missing, the worst case will be assumed.

A by-patient listing of all adverse events (including non-treatment-emergent events) will be provided. This listing will include center, patient identifier, age, race, adverse event (SOC, PT, and verbatim term), date of onset, date of resolution, duration, CTCAE, seriousness, action taken, outcome and causality.

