4.15.2 Deaths, Serious Adverse Events, and Other Significant Adverse Events

Deaths, SAEs, and Other Significant AEs will be listed and summarized if numbers allow. The following summaries are planned.

- A summary of the number and percentage of TEAE leading to death
- A summary of the number and percentage of patients reporting a serious TEAE, by SOC and PT
- A summary of the number and percentage of patients with TEAEs leading to discontinuation of study treatment, by SOC and PT

The following listings will be created:

- A by-patient listing of all deaths that occurred during the study
- A by-patient listing of all SAEs
- A by-patient listing of all AEs leading to discontinuation of study treatment

Listings will follow the format described for AEs in Section 4.15.2.

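### Read literally, the SAP ranks a missing CTCAE grade above Grade 5, so an ungraded record can replace a recorded severe grade in the by-severity adverse event table

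*SAP*

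**What the plan says.** SAP 4.15.1 plans one adverse event summary by severity: "A summary of the number and percentage of patients reporting a TEAE by Common Terminology Criteria for Adverse Events (CTCAE) grade, SOC and PT". Three sentences in the same section decide what enters it and its companion table by causality.

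- Attribution: "For each patient and each adverse event, the worst CTCAE Toxicity grade (Version 5) recorded will be attributed and used in the by-severity summaries".
- Missing grade: "If CTCAE is missing for, the missing category will be used as worst category".
- Missing causality: "If causality is missing, the worst case will be assumed".

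Protocol 12.1.1 grades severity with CTCAE Version 5 (Table 3) and provides a fallback: "If the experience is not covered in the CTCAE criteria, the guidelines shown in" Table 4 apply. Both tables number severity from 1 to 5. The SAP names only the CTCAE grade and does not mention Table 4.

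Protocol 16.6 gives no rule for severity grades. SAP section 1 says that the SAP prevails where the two documents differ. SAP 4.15.1 is therefore the only text that governs the point.

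**The concern.** A rule phrased in terms of the worst category is normally meant to be conservative, so that a gap in the data never makes the product look safer. This one appears to work the other way. Missing is not converted into a severe grade. It remains a separate category and is placed at the top of the ranking, so it outranks grades that were actually recorded. A patient whose severe event is documented can drop out of the severe rows because a second record carries no grade.

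Safety is a listed secondary endpoint, and this is the only planned adverse event summary by severity. Protocol 12.1.1 itself points out that severe and serious are different things. A non-serious Grade 3 event moved to Missing would not reappear in the serious-event summary, and it could be identified as severe only from the by-patient listing.

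**Working it through.** The plan states no figure on this point and no power or alpha formula applies. The check is to apply the SAP sentence to small sets of records and compare it with the alternative rule.

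**Inputs (SAP 4.15.1).** The unit of attribution is the patient and the adverse event. The ranking is Grade 1 < 2 < 3 < 4 < 5, with Missing placed as worst.

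**Rule A, literal.** If any record in the unit has no grade, the result is Missing. Otherwise it is the maximum grade.

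**Rule B, recorded grades first.** The result is the maximum of the non-missing grades, and Missing only if there are none.

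| Records in the unit | Rule A | Rule B |
|---|---|---|
| Grade 3 and ungraded | Missing | 3 |
| Grade 4 and ungraded | Missing | 4 |
| Grade 5 and ungraded | Missing | 5 |
| Grade 1 and ungraded | Missing | 1 |
| Ungraded only | Missing | Missing |
| Grade 3 and Grade 1 | 3 | 3 |

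The two rules differ only where graded and ungraded records share a unit. In every such case Rule A discards the recorded grade. No combination under Rule A moves a patient into a higher numbered grade. The count in the severe rows can therefore fall but cannot rise.

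**Level of the row.** Suppose a patient has a Grade 3 record of preferred term (PT) A and an ungraded record of PT B in the same SOC.

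- PT A row: Grade 3 under both rules. An ungraded record of a different term does no harm here.
- PT B row: Missing under both rules.
- SOC row and overall row: Missing under Rule A and Grade 3 under Rule B, provided the rule is carried up to these rows. The SAP sets the unit as patient by event and does not say what happens at higher levels.

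**Contrast with causality.** The neighbouring sentence replaces a missing causality with a real value, the most related one. That moves the patient into the category of concern. The grade sentence moves the patient out of all numbered categories. Two adjacent rules with similar wording thus act in opposite directions.

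**Can the unit hold more than one record?** Attributing a worst grade to each patient and event presupposes that it can. The TEAE definition also covers events that worsen in severity, which may produce more than one record of the same event.

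**The case against.** The strongest reply is that the sentence is visibly incomplete, because the object after the word for is absent. The sentence that governs attribution speaks of the worst grade *recorded*. A missing grade is not a recorded grade, so Missing may be meant only as a fallback row when nothing was recorded. That reading is possible and sensible. However, it rests on one word, and the sentence on missing grades omits the condition that would establish it. Two programmers could reasonably produce different tables, so the text needs correction on either reading.

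Other parts of the reply stand and limit the point.

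- **Other outputs are unaffected.** Serious TEAEs have their own summary ("A summary of the number and percentage of patients reporting a serious TEAE, by SOC and PT"), as do TEAEs leading to death, and deaths and SAEs are listed by patient. SAP 4.15.1 also promises a complete listing that shows the CTCAE grade: "A by-patient listing of all adverse events (including non-treatment-emergent events) will be provided". A reader might infer that fatal or serious events could vanish from the safety report. The documents do not support that.
- **Ungraded records are not shown to be likely.** A reader might infer from Table 4 that events outside CTCAE will arrive without a grade. Table 4 assigns grades on the same 1 to 5 numbering, Protocol 9.1.9 and 12.1 require severity or grade to be recorded, and Protocol 17.3 provides for data checks and queries. Whether a Table 4 grade would be stored as a missing CTCAE value depends on the eCRF, which is not among the documents. What remains is that the SAP does not say how Table 4 grades enter the summary.
- **The same-term case should be uncommon.** There is a single injection, and TEAEs are limited to Day 4.
- **No percentage is supported.** A reader might start from the 35 of 558 men (6.3%) in Protocol 2.1.2, suppose a handful of severe cases, and quote the loss of one as a large relative error. That figure counts any AE or SAE over 30 days, not severe events up to Day 4. The number of severe cases and the loss of one would both be assumptions.

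**Conclusion.** The point holds in a limited form. As written, SAP 4.15.1 ranks a missing CTCAE grade above Grade 5. Where a patient has a graded and an ungraded record of the same event, the recorded grade is replaced by Missing. The same follows in SOC and overall rows only if the rule is applied there, which is unstated. The direction is certain on the literal reading: severe events in this table can be understated and never overstated.

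The size is one patient per affected row for each such case. The number of cases is unknown and probably small. The consequence is confined to one descriptive table, and no hypothesis test or success criterion is involved. The conclusion assumes the literal reading and at least one patient with graded and ungraded records in the same unit. It is worth correcting because the rule works against its apparent purpose and the correction is nearly free.

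**What to change.** Replace the sentence on missing grades in SAP 4.15.1 with:

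> The highest non-missing grade is used; a patient enters the Missing row only if no grade was recorded for that patient at that level (PT, SOC, overall). Grades assigned with protocol Table 4 enter the same 1 to 5 scale.

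This keeps every recorded grade, settles the unit for the higher-level rows, and closes the gap on Table 4. There is no need to impute a particular severe grade to ungraded events: any chosen grade would be arbitrary, and the Missing row together with the listing already shows them.

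The cost is a short text change and the matching line of table code, with no new data.

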4.15.2 Deaths, Serious Adverse Events, and Other Significant Adverse Events

Deaths, SAEs, and Other Significant AEs will be listed and summarized if numbers allow. The following summaries are planned.

- A summary of the number and percentage of TEAE leading to death
- A summary of the number and percentage of patients reporting a serious TEAE, by SOC and PT
- A summary of the number and percentage of patients with TEAEs leading to discontinuation of study treatment, by SOC and PT

The following listings will be created:

- A by-patient listing of all deaths that occurred during the study
- A by-patient listing of all SAEs
- A by-patient listing of all AEs leading to discontinuation of study treatment

Listings will follow the format described for AEs in Section 4.15.2.

4.15.3 Clinical Laboratory Evaluation

Blood safety laboratory values (hematology, biochemistry and coagulation) will be listed by patient and study time point including changes from baseline. The baseline for the laboratory values will be the pre-dose results obtained on Day 1.

PAREXEL International

Blue Earth Diagnostics
BED-PSMA-301

Statistical Analysis Plan

All values outside the clinical reference ranges will be flagged in the data listings. The abnormal values will be flagged with 'L' for values below the lower limit of the clinical reference range and 'H' for values above the upper limit of the clinical reference range and included in the listings.

Descriptive statistics (for non-categorical data including hematology and blood chemistry) will be presented for both individual values (N, mean, SD, median, minimum, maximum) and changes from baseline.

The following summaries will be provided:

- A summary of each laboratory parameter at visit 2 (pre-dose at day 1) and visit 3
- A summary of the change from baseline to visit 3 in each laboratory parameter
- A shift table of the number and percentage of patients experiencing treatment-emergent laboratory abnormalities at baseline vs visit 3, by laboratory parameter

4.15.4 Vital Signs, Physical Findings and Other Observations Related to Safety

Vital signs will be listed, including change from baseline. Baseline will be the last assessment before dosing, this is planned to be Visit 2 (Day 1), but may be any other assessment.

A summary of each vital sign parameter, including change from baseline to visit 3 will be given.

12-lead ECG results will be listed, including change from baseline by patient and time point. Baseline will be the pre-dose assessment at Visit 2 (Day 1). A summary of each ECG parameter, including change from baseline to visit 3 will be given.

Physical examinations results (Normal, Abnormal Not Clinically Significant, Abnormal Clinically Significant) will be listed by patient and time point. Physical examination findings will be summarized by visit.

Heart rate category (<40 bpm, 40-59 bpm, 60-100 bpm, 101-130 bpm, >130 bpm) will be summarized and a shift table will be presented.

Shift tables will be presented for QTc and physical examinations.

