9.1 Clinical Assessments**9.1.1 *Concomitant Medications***

All concomitant medication and concurrent therapies will be documented at screening, with any changes in concomitant medication during the study recorded on the eCRF. The dose, route, unit frequency of administration, and indication for administration and dates of medication will be captured.

9.1.2 *Demographics*

Demographic information (full/partial date of birth/age, gender, ethnicity/race, sex, height, weight, as permitted by local regulations) will be recorded at screening. Weight will also be recorded pre-IP administration on the day of the rhPSMA-7.3 (¹⁸F) injection.

9.1.3 *Medical History*

Relevant medical history, including history of current disease, concomitant disease record, information regarding underlying diseases will be recorded at screening. Histological confirmation of adenocarcinoma of the prostate must be provided at screening.

If not already performed within 60 days prior to screening, conventional imaging as part of routine clinical practice, which may include bone scan (^{99m}technetium-hydroxydiphosphate [^{99m}Tc-HDP], ^{99m}technetium-methyldiphosphonate [^{99m}Tc-MDP]), abdominal/pelvic CT or MRI, and chest CT as per local practice) will be performed. Conventional imaging that has been performed at non-participating institutions will be accepted provided the scans are retrievable and reviewed by the participating institution.

Note: baseline conventional imaging performed as part of routine clinical practice should be performed at least 24 hours prior to the investigational rhPSMA-7.3 (¹⁸F) PET scan.

9.1.4 *Physical Examination*

A focused physical examination will be performed by an appropriately licensed and credentialed clinician at screening and at the safety follow-up visit within 1 to 3 days post-IP administration (may occur within 1 to 5 days post-IP administration due to the COVID-19 pandemic). New abnormal physical exam findings must be documented on the eCRF. Any clinically significant changes (as determined by the site investigator) in physical examination findings should be reported as an AE.

9.1.5 *Vital Signs*

Vital signs (body temperature, blood pressure, pulse and respiration rates) will be recorded after resting for 5 minutes at screening and pre- and post-IP administration on the day of rhPSMA-7.3 (¹⁸F) injection.

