10.2 Visit 2 (Day 1; IP Administration)

1. Record any changes in concomitant medication since screening (omit if Visit 1 and Visit 2 are combined; see [Section 10.3](#)).
2. Perform and record pre-IP administration vital signs.
3. Record patient's body weight pre-IP administration.
4. Perform 12-lead ECG pre-IP administration.
5. Perform baseline blood safety laboratory tests as outlined in [Section 9.2](#).
6. Ask about and record any AEs since screening (omit if Visit 1 and Visit 2 are combined; see [Section 10.3](#)).
7. IP administration (IV bolus rhPSMA-7.3 (¹⁸F) injection).
8. PET scan as described in the Study Imaging Manual.

9. Record any AEs occurring during the scan process.
10. Perform and record post-IP administration vital signs.
11. Schedule patient for Visit 3 within 1 to 3 days post-IP administration.

Note: pre-IP administration ECG and blood safety laboratory tests may be performed at Visit 1 if: a) not feasible at the Visit 2 imaging center and b) collected up to 48 hours before IP administration where Visit 1 and Visit 2 are not combined.

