10.4 Visit 3 (Day 2 to 4; Follow-up Visit)

1. Perform clinical review of imaging results and discussion of further procedures/treatments with the patient.
2. Record any AEs and changes in concomitant medication since Visit 2.
3. Perform a focused physical examination.
4. Perform repeat blood safety laboratory tests as outlined in [Section 9.2](#).
5. Perform 12-lead ECG.
6. Schedule patient to receive treatment within 45 days post-IP administration.

Notes:

- a. in cases where the rhPSMA-7.3 (¹⁸F) PET imaging results are not available at this visit, the imaging results and further procedures/treatment plan should be reviewed with the patient within 7 days after rhPSMA-7.3 (¹⁸F) imaging (this may be conducted by telephone at the clinician’s discretion).
- b. to ensure patient safety due to the COVID-19 pandemic, the post-IP safety follow-up (laboratory and ECG assessments and focused physical examination) may be conducted within 1 to 5 days post-IP administration.

Patients will remain in the study until the results of the histology or confirmatory imaging are obtained in order to satisfy the SoT.

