*** The patient should receive treatment within 45 days (may be extended up to 60 days due to the COVID-19 pandemic) post-IP administration, with treatment decision based on rhPSMA-7.3 (¹⁸F) PET imaging and conventional imaging (see k below).

a To include medical history and concomitant disease record, including a history of PCa, diagnosis date and prior PCa treatments, as well as histological confirmation of adenocarcinoma of the prostate.

b Pre-IP administration.

c Vital signs to be recorded pre-IP administration and post-IP administration.

d To be performed pre-IP administration.

e If not already performed within 60 days prior to screening, conventional imaging will be performed as part of routine clinical practice, which may include bone scan (^{99m}Tc-HDP, ^{99m}Tc-MDP), abdominal/pelvic CT or MRI, and chest CT as per local practice). Note: Conventional imaging that has been performed at non-participating institutions will be accepted provided the scans are retrievable and reviewed by the participating institution. Note: baseline conventional imaging performed as part of routine clinical practice should be performed at least 24 hours prior to the investigational rhPSMA-7.3 (¹⁸F) PET scan.

f Baseline blood safety laboratory tests, including hematology (full blood count), biochemistry (urea and electrolytes, liver function tests) and coagulation to be performed pre-IP administration.

g AEs will be monitored and recorded from the time of informed consent until the last study visit.

h For full details see the Study Imaging Manual.

- i To discuss imaging results and further procedures/treatments with the patient (all patients).
- j If rhPSMA-7.3 (¹⁸F) PET does not detect M1 disease, the patient will undergo the scheduled RP and PLND. In patients without M1 lesions identified and in whom the patient and physician believe, after obtaining the results of the rhPSMA-7.3 (¹⁸F) PET, that EBRT would be a better therapeutic option than RP, the patient may proceed to EBRT and the rationale for this change of management will be documented on the eCRF.

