3.2.4 Safety Variables

In all patients, safety evaluations will include AE monitoring and reporting from the time of informed consent throughout the study.

Vital sign assessments will also be conducted at screening and pre- and post-IP administration on the day of rhPSMA-7.3 (¹⁸F) injection.

In addition, a focused physical examination will be performed at screening and at the safety follow-up visit within 1 to 3 days post-IP administration (may occur within 1 to 5 days post-IP administration due to the COVID-19 pandemic), and a 12-lead ECG will be performed pre-IP administration on the day of rhPSMA-7.3 (¹⁸F) injection and at the safety follow-up visit within 1 to 3 days post-IP administration (may occur within 1 to 5 days post-IP administration due to the COVID-19 pandemic). Baseline blood safety laboratory tests, including hematology (full blood count), biochemistry (urea and electrolytes, liver function tests) and coagulation will be performed pre-IP administration on the day of rhPSMA-7.3 (¹⁸F) injection and repeated at the safety follow-up visit within 1 to 3 days post-IP administration (may occur within 1 to 5 days post-IP administration due to the COVID-19 pandemic).

4 STATISTICAL METHODS**4.1 Data Quality Assurance**

All tables, figures and data listings to be included in the report will be independently checked for consistency, integrity and in accordance with standard Parexel procedures.

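### The SAP ties vital-sign change from baseline to Visit 3, where no vital signs are scheduled, and names no summary of the post-injection Day 1 values

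*SAP*

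**What the plan says.** SAP 4.15.4 plans two displays specific to vital signs. The first is a by-patient listing: "Vital signs will be listed, including change from baseline". The second is a table: "A summary of each vital sign parameter, including change from baseline to visit 3 will be given". The baseline is defined there as follows: "Baseline will be the last assessment before dosing, this is planned to be Visit 2 (Day 1), but may be any other assessment".

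The collection schedule is set elsewhere. Protocol 9.1.5, which places the last two readings on Day 1, states: "Vital signs (body temperature, blood pressure, pulse and respiration rates) will be recorded after resting for 5 minutes at screening and pre- and post-IP administration". The Visit 2 steps in Protocol 10.2 end the imaging day with the instruction "Perform and record post-IP administration vital signs", and footnote c to the Appendix 1 schedule says of the Visit 2 entry: "Vital signs to be recorded pre-IP administration and post-IP administration". SAP 3.2.4 repeats the protocol's time points: "Vital sign assessments will also be conducted at screening and pre- and post-IP administration on the day of" injection.

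Protocol 16.6 promises a summary of change from baseline for laboratory tests, vital signs and ECG, and names no visit. SAP section 1 says that the SAP prevails where the two documents differ.

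**The concern.** The time point that the SAP names for vital-sign change is one at which the trial does not schedule vital signs. The time point at which it does schedule them after dosing is not named in any summary. Vital signs are a component of secondary endpoint 8. The comparison of values before and after injection on Day 1 is the only vital-sign contrast around dosing that the schedule supports. Read literally, the SAP does not deliver the change-from-baseline summary that Protocol 16.6 commits to.

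Two features add some weight. SAP 4.14.1.3 plans an interim safety analysis on the first 150 patients, so the same wording may affect two sets of output. There is also no data monitoring committee (Protocol 15; SAP 4.15.6), so the prespecified tables are the main aggregate view of safety.

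**Working it through.** The plan gives no figure to reproduce, so the check sets each statement of when vital signs are taken beside the planned summary.

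| Source | Screening | Day 1 pre-injection | Day 1 post-injection | Visit 3 |
|---|---|---|---|---|
| Protocol 5.4 | yes | yes | yes | not named |
| Protocol 9.1.5 | yes | yes | yes | not named |
| Protocol 10.1 (Visit 1) | yes (omitted if Visits 1 and 2 are combined) | – | – | – |
| Protocol 10.2 (Visit 2) | – | step 2 | step 10 | – |
| Protocol 10.4 (Visit 3) | – | – | – | six steps, none for vital signs |
| Protocol Appendix 1, vital-signs row and footnote c | marked | marked | marked | no mark |
| SAP 3.2.4 | yes | yes | yes | not named |

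1. Scheduled measurements per patient: up to 1 at screening, 1 pre-injection, 1 post-injection and 0 at Visit 3. The Visit 3 steps in Protocol 10.4 include a focused physical examination, laboratory tests and an ECG. The Appendix 1 note on Visit 3 lists the same three safety assessments.
2. Baseline under SAP 4.15.4 is the last pre-dose value, planned for Visit 2. A change score also needs a post-dose value, and the schedule supplies exactly one, post-injection on Day 1.
3. Change from baseline to Visit 3 needs a Visit 3 value. With none scheduled, that component has n = 0, apart from any unscheduled measurements.
4. Change from baseline to post-injection on Day 1 can be computed for every patient with both readings, but no summary names it.
5. The heart-rate category summary and shift table in SAP 4.15.4 do not fill the gap. They name no time point, do not say whether the source is the pulse or the ECG, and leave out blood pressure, temperature and respiration rate.
6. By contrast, SAP 4.15.3 names Visit 2 pre-dose and Visit 3 for laboratory tests, and the ECG sentence in SAP 4.15.4 refers to Visit 3. Both assessments are scheduled at Visit 3, so those sentences can be carried out as written.

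The SAP therefore conflicts with its own section 3.2.4 as well as with the protocol schedule. The vital-sign sentence matches the ECG sentence closely, so text may have been carried over, but that is an inference.

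**The case against.** The strongest reply is that the sentence promises, first, a summary of each parameter, and that the Visit 3 change is only one item within it. Values at screening and at both Day 1 time points can fill that summary. Protocol 16.6 names no visit, so its commitment to summarise change can only mean the Day 1 post-injection value. SAP 4.15.4 does not exclude such a summary, and SAP 4.17 records no change to the vital-sign analysis. The table shells, to which SAP 4.14.1.3 refers, are not among the documents and may already carry the right time point.

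Much of this stands. A reader might infer that the vital-sign table would be empty or that the analysis would return no data. The documents do not support that, because only the Visit 3 change component lacks scheduled data. A reader might also infer that an acute reaction could go unreported. That is not supported either:

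- post-injection values are listed by patient with change from baseline;
- clinically significant vital-sign changes are to be reported as adverse events (Protocol 9.1.5);
- adverse events during the scan are recorded (Protocol 10.2);
- treatment-emergent events are tabulated (SAP 4.15.1);
- injection site reactions have their own summary (SAP 4.15.5).

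The narrower point remains. The only change that the SAP names cannot be computed from the schedule. A listing is not the summary promised in Protocol 16.6, and adverse-event reporting captures the cases that an investigator judges significant, not the overall distribution. If the shells are right, the SAP text should be made to agree with them.

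**Conclusion.** The inconsistency is real and should be corrected before the safety tables are produced. As written, the Visit 3 vital-sign change has no scheduled data in any patient, and the one scheduled post-baseline measurement has no named summary. The consequence is limited to descriptive safety reporting within secondary endpoint 8. No hypothesis test, analysis population, data collection or co-primary result is affected, and no values are lost.

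The conclusion assumes that sites follow the protocol schedule. Unscheduled Visit 3 readings could give the Visit 3 change a few values, but not a planned sample. It also rests on the SAP text alone, since the shells could not be examined.

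**What to change.** Replace the vital-sign summary sentence in SAP 4.15.4 with wording such as: *Each vital sign parameter will be summarised at every scheduled time point (screening, pre-IP and post-IP on Day 1), with change from baseline to post-IP on Day 1.*

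Keep the existing baseline definition. A change defined strictly as pre-IP to post-IP would discard its fallback, and patients without a Day 1 pre-dose value would then have no change score. Naming screening keeps those values in the summary. Leave change to Visit 3 in place for ECG and laboratory tests.

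The cost is one SAP sentence and a check that the corresponding table shell, including any interim version, agrees with it. No new data or change to the assessment schedule is needed.
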